3.2 Study Duration, Enrollment and Sites

The proposed study will be completed within three years and will include pregnant women from all KP facilities in the Northern California Region. Start-up will occur during the first three months and will involve obtaining IRB approval, hiring staff, training, conducting focus group interviews, testing data collection materials, developing and revising interview instruments (including the questionnaire) for stage-two data collection of information on confounders, establishing mechanisms for identification of eligible subjects through the EMR. Data collection (including data linkage, recruitment and conducting interviews) will be ongoing from month 4 through month 30. Ascertainment of diagnosis and treatment of genital herpes and pregnancy outcomes will continue from month 4 through month 35. Data cleaning and analysis as well as report writing will be carried out during the last 4 months. The timeline for activities involved in the study is as follows:

Months 1-3	
 Obtain IRB approval. Hire staff. Train interviewers. Set-up tracking database. Develop algorithm for identifying eligible participants. Create interview instruments including questionnaire and instructions, operations manual, and pilot test questionnaire. Conduct focus group interviews.
Months 4-30	
 Identify and include eligible pregnant women for the stage-one sample. Conduct data linkages Classify 90,000 women from stage-one sample into treatment categories based on their genital herpes infection status and treatment. Select a random sample of 300 from each category to form the stage-two subsample. Conduct telephone interviews with stage-two subsamples.

Months 4-35 Ascertain outcomes of interest.

Months 33-35 Clean data, conduct and complete data analyses, and prepare final report.

Months 35-36 Create materials for dissemination of the findings.
Dissemination of the findings, which will continue beyond month 36.

3.3 Study Population

3.3.1 Inclusion Criteria

- 1) Females \geq age 18
- 2) Kaiser members
- 3) Pregnant beyond 20 weeks of gestation during the recruitment period
- 4) Cohort A: pregnant women with genital herpes who are treated before the 3rd trimester

Cohort B: pregnant women with genital herpes who are treated after the 3rd trimester

Cohort C: pregnant women with genital herpes, but untreated

Cohort D: pregnant women with neither genital herpes nor receiving anti-herpes medications

3.3.2 Exclusion Criteria

- 1) <18 years old
- 2) Not Kaiser Permanente members
- 3) Not pregnant.
- 4) Not meeting the definition for the 4 cohorts (pregnancy and HSV/treatment status).

Subjects that do not meet all of the enrollment criteria may not be enrolled.

3.3.3 Populations

Stage I population

All KPNC women aged 18 years (the minimum age required by our KPNC IRB) or older who are pregnant beyond 20 weeks of gestation during the recruitment period will be included to form the Stage I population, estimated at 90,000. These women will be assigned to one of the four cohorts based on diagnosis and treatment of genital herpes infection. Identification of genital herpes will be based on information from multiple databases captured by KPNC EMR including clinical diagnosis, laboratory testing and viral culture, prenatal screening inventory, and medical history. Treatment will be determined through prescription and dispensing of anti-herpes medications from the pharmacy data. Based on the combination of infection and treatment as well as the specific aims, we expect to establish four cohort groups. information currently available information, we expect a total of 2,100 women with genital herpes receiving treatment before the 3rd trimester (Cohort A), 2,100 women with genital herpes receiving treatment after the 3rd trimester (Cohort B), 6,600 women with untreated genital herpes (Cohort C), and 79,200 controls with neither genital herpes nor treatment (Cohort D), as shown in Figure 1. A small adjustment may need to be made at the end of pregnancy, if the status of the infection and/or treatment has changed since the initial assignment to each comparator (e.g., from untreated to treated). Through the KPNC EMR, we will have information on genital herpes infection and treatment during pregnancy (the exposure variables), and PTD and LBW (the outcome variables) (Table 4) as well as many potential confounders (Table 5) for all 90,000 pregnant women. This large Stage I population will provide a large powerful study population to examine comparative effectiveness of genital herpes treatment in reducing adverse pregnancy outcomes, addressing the questions listed in the specific aims.

Stage II samples

A sample of 300 pregnant women from each of the four cohorts described above (Figure 1) will be randomly selected to form Stage II samples. The random selection will be spread evenly throughout the study period so that all of the estimated 90,000 participants in Stage I will have an equal chance of being selected. They will be selected after their inclusion in Stage I with known status of infection and treatment, mostly before the 3rd trimester to avoid interviewing after delivery to reduce participation and recall biases. Infection status will largely be known in the 1st or early 2nd trimester after the universal STD screening. Any change in exposure status (infection and treatment) after initial assignment will be rectified and finalized during analyses, as we have done in other similar studies with two-stage design (with different exposures in pregnancy).

Participants in Stage II samples will be interviewed to obtain more detailed information on characteristics of genital herpes infection, including history of the infection (e.g., age at initial infection, history of recurrence and treatment), whether it is a primary or latent infection, symptomatic or asymptomatic, etc. While our EMR has information on some of these characteristics of the infection, especially those ascertained through the prenatal screening tool, this Stage II interview will provide us additional characteristics of the infection to allow for assessment and thus to examine whether the treatment effectiveness varies depending on those infection characteristics (e.g., more effective for recent vs. past infection, and age at onset of initial infection, etc.).

The Stage II samples will also allow for direct ascertainment of compliance with prescribed medications. Studies based on pharmacy data alone usually have to make an assumption of 100% compliance with dispensed medications. In this study, we can directly examine the compliance and assess its potential impact on treatment effectiveness. This will be an important strength for this pharmacoepidemiologic study.

In the Stage II samples, we will conduct structured interviews to ascertain detailed information on the history of genital herpes, detailed characteristics of the infection including age at initial infection, history of recurrence and treatment, primary or latent infection, symptomatic or asymptomatic, and severity. This in-depth collection of additional information will allow for further examination of the comparability of underlying infection between treated and untreated groups, and more accurate assessment of treatment effectiveness after more thorough control for the impact of these differences in underlying infections. In addition, it will allow us to assess factors (e.g., infection characteristics) that may impact the treatment effectiveness.

Through the interview, we will also directly ascertain compliance to prescribed medications for treating genital herpes. We will make appropriate adjustment for compliance ratio in data analysis to more accurately estimate the treatment effectiveness after taking into account of non-compliance. In addition, we will also ascertain additional confounders including multivitamin intake during pregnancy and physical activity.

Informed consent will be obtained before the interview. All contact procedures will follow the standard contact and recruitment procedures as required by KPNC's IRB. All participating women will be reimbursed \$40 their time and out of pocket expenses. Based on our experience with similar studies among KPNC pregnant women, a participation rate of 70-75% among eligible pregnant women can be expected. The recruitment will continue until 300 subjects from each of the four cohort groups have completed the interview.

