Point and interval estimates of the relative hazards of PTD associated with first treatment during pregnancy before and first treatment during the 3rd trimester will be obtained (Cohort A vs. B) by extending the Aim 1 regression model to capture treatment timing. Parameter estimation, the approach to inclusion of potential confounders, modeling of continuous covariates, and model diagnostics are as described above for Aim 1 analyses. Treatment will be handled as a time-varying covariate for proper classification of exposure status in each risk set for the Cox regression (three levels: no treatment, first treatment < 3rd trimester, treatment in 3rd trimester). Significance of the difference between strength of association across the two treatment timing categories will be assessed via a Wald test.

Aim 3. Do other treatment metrics, including treatment duration, dosage, and compliance, impact treatment effectiveness in reducing PTD and LBW risk?

Metrics of treatment exposure of interest will be treated as time-dependent covariates in Cox regression analyses to account for changes in exposure status during follow-up, including cumulative duration (categorized as no use, 1-5 days, 6-10 days, 11-30 days, and > 30 days) based on clinical prescription patterns, and cumulative dose (categorized as no use, 1-4,800mg, 4,801-12,000mg, and >12,000 mg) also based on current clinical prescription patterns. In addition to examining these metrics in relation to pregnancy outcomes during the entire pregnancy, we will also assess trimester-specific measures of treatment duration and dose.

Aim 4. Does treatment effectiveness vary depending on the type (or severity) of underlying genital herpes infection? (e.g. treating symptomatic genital herpes infection vs. treating latent/asymptomatic genital herpes)

Analyses will examine potential heterogeneity in association between treatment and PTD across infection characteristics via the inclusion of appropriate cross-product terms and a likelihood ratio test, and point and interval estimates of association at each level of the effect modifier will be obtained via appropriate transformed linear combinations of regression parameter estimates.

Aim 5. Does genital herpes infection in pregnancy, if untreated, increase the risk of PTD and LBW, compared to no genital herpes infection? (untreated vs. controls without genital herpes) .

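### Infection status may be revised up to the end of pregnancy with no dating rule for a herpes record, so the plan does not prevent a late or delivery-time record from setting a woman's cohort for the whole pregnancy

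*Combined protocol and SAP*

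**What the plan says.** **Revision of status.** Section 3.3.3 (Stage I population) states: "A small adjustment may need to be made at the end of pregnancy, if the status of the infection and/or treatment has changed". The Stage II text in the same section adds: "Any change in exposure status (infection and treatment) after initial assignment will be rectified and finalized during analyses". Both sentences cover infection as well as treatment.

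**Sources and window.** "Identification of genital herpes will be based on information from multiple databases captured by KPNC EMR"; the list covers diagnosis, laboratory testing and culture, prenatal screening and medical history. Section 3.2 gives diagnoses and outcomes the same calendar window: "Ascertainment of diagnosis and treatment of genital herpes and pregnancy outcomes will continue from month 4 through month 35". The cohort definitions in Section 3.3.1 date the treatment relative to the 3rd trimester but do not date the infection. Cohort D requires absence of genital herpes, so a woman recorded late cannot finish in D.

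**Models.** Section 4.2, Aim 2: "Treatment will be handled as a time-varying covariate for proper classification of exposure status in each risk set for the Cox regression", with "three levels: no treatment, first treatment < 3rd trimester, treatment in 3rd trimester". Aim 3 treats the treatment metrics as time-dependent. Aim 5 is Cohort C versus D by Cox regression, with no mention of time-varying infection. LBW is analysed by logistic regression in Aims 1-5. Section 3.1 says in general terms that the PTD Cox model will accommodate delayed entry and time-dependent covariates, without listing them.

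**Limiting text.** The sentence just before the Stage II rule reads: "Infection status will largely be known in the 1st or early 2nd trimester after the universal STD screening". The Stage I sentence calls the adjustment small, and its one example is a treatment change.

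**The concern.** A final infection label can use information that arises after follow-up starts at 20 weeks. If that label is then treated as fixed from entry, two distortions are possible in women who move into the infected cohorts through late recording.

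1. **Event-free time.** A woman first recorded at 35 weeks must still have been pregnant at 35 weeks. Counting her as infected from 20 weeks credits the infected group with weeks in which she could not have had the event. This lowers the apparent PTD risk in untreated infection, and so lowers the Aim 5 hazard ratio.
2. **Outcome-prompted recording.** If a preterm delivery itself leads to a first herpes record, the outcome contributes to the exposure label. This raises the apparent risk and can produce an Aim 5 association where none exists.

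Aim 5 (C versus D) is most exposed because infection status defines the contrast. Aims 1 and 2 are affected only so far as late recording differs among A, B and C. The two distortions act in opposite directions, and the final estimate would not show how much of each it contains. Section 4.1 itself sets the principle that covariates are assessed before the outcome, and end-of-pregnancy revision of infection departs from it.

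**Working it through.** **Inputs from the plan.** Cohort C 6,600 and Cohort D 79,200 (Section 3.3.3); PTD 8% (lower end, Section 4.5); effective size 1,200 per category, two-sided alpha 0.05, power 0.80, Aim 5 detectable HR 1.51 (Section 4.5, Table 6).

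**The plan's own figure.** Taking 8% as the overall rate, events = 2,400 x 0.08 = 192. Detectable HR = exp[(1.960 + 0.842)/sqrt(192/4)] = 1.498, and power at 1.51 is 0.815. Table 6 is reproduced and is not in dispute; 1.51 serves below only as a reference value.

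**Distortion 1, by arithmetic.** Assumed, not in the documents: PTD timing of 6/12/14/68% in weeks 20-28/28-32/32-34/34-37; first-record week uniform over 28-39; a share f of Cohort C recorded late.
- Mean share of PTD risk already passed at the record date = (4 x 0.12 + 2 x 0.25 + 3 x 0.66 + 2 x 1.00)/11 = 4.96/11 = 0.451.
- Apparent HR = 1.51 x (1 - 0.451f).

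| f | Apparent Aim 5 HR |
|---|---|
| 1% | 1.50 |
| 3% | 1.49 |
| 5% | 1.48 |
| 15% | 1.41 |

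**Distortion 1, by simulation.** 90,000 pregnancies were followed from 20 weeks and censored at 37 weeks, with 8% PTD, using an interval-stratified Mantel-Haenszel rate ratio as an approximation to Cox. Late shares and record weeks are again assumed.

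| True HR | Late share | Coded from entry, records 28-39 wk | Coded from entry, records 36-39 wk | Coded from record date |
|---|---|---|---|---|
| 1.0 | 5% | 0.98 | 0.96 | 1.00-1.01 |
| 1.0 | 10% | 0.95 | 0.90 | 1.00 |
| 1.0 | 20% | 0.90 | 0.81 | 1.00-1.01 |
| 1.5 | 10% | 1.43 | 1.35 | 1.50 |

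Dating infection from its record removes the distortion.

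**Distortion 2.** Assume no true effect, with 8% PTD in both cohorts (528 events in C, 6,336 in D). Suppose 1% of D's preterm and 0.5% of its term deliveries are first recorded as infected at delivery.
- Moved: 79,200 x 0.08 x 0.01 = 63 preterm; 79,200 x 0.92 x 0.005 = 364 term.
- C = (528 + 63)/(6,600 + 427) = 8.41%; D = (6,336 - 63)/(79,200 - 427) = 7.96%; ratio 1.06.
- With no term women moved: 8.87%/7.93% = 1.12.
- With 1% of both moved: 1.00.

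On crude Stage I counts, with pooled SE = sqrt[0.08 x 0.92 x (1/n_C + 1/n_D)], the shift to 1.06 is z = 0.00452/0.00338 = 1.34. That raises the chance of a significant result under no effect from 5% to about 27%. The shift to 1.12 is z = 0.00948/0.00346 = 2.74, or about 78%. The adjusted two-stage estimator would be less precise, so these are upper guides.

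**Cost of dating the record.** Suppose 10% of C (660 women) were counted in D throughout, which overstates the effect because D would hold them only until the record date. With a true ratio of 1.51 (rate 12.08%), D's rate becomes (6,336 + 660 x 0.1208)/79,860 = 8.03%, and the ratio becomes 12.08/8.03 = 1.50.

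**The case against.** A reader might infer that a late record **is** applied to the whole pregnancy and that the infected cohorts **are** therefore defined partly by the outcome. The documents do not support that for PTD. No sentence states a back-dating rule, and Section 3.1 allows delayed entry and time-dependent covariates, so infection could be dated correctly within the stated model. Aim 2 names treatment because Aim 2 is about treatment timing; this does not show that infection is fixed in Aim 5. This part of the objection stands.

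The size is also limited by the plan's own text on early screening and a small adjustment. It gives no number for either, so this limits the likely size without settling it.

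No passage describes a culture or examination prompted by preterm labour. Distortion 2 is a possibility with invented rates, and equal recording at term and preterm deliveries removes it. The 1.06 case needs 427 newly labelled women, 6% of the final Cohort C; the 1.12 case needs no term delivery ever to be newly recorded. The two distortions could also offset: 1.06 x (1 - 0.451 x 0.10) = 1.01. That cannot be assumed, nor checked from the result.

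Table 4, cited beside the exposure and outcome variables, is not in the text available here, so a dating rule there cannot be excluded.

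Finally, Section 1 describes the virus as permanent, so a late record often reveals an infection already present, and dating it leaves some infected time in D. True, but the calculation above shows the dilution to be slight.

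None of this helps LBW: a logistic model cannot let exposure vary in time, so a landmark or final status must be chosen.

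**Conclusion.** The point holds as a gap in a stated rule. The plan provides for infection status to be revised at the end of pregnancy and finalised at analysis, but does not date the qualifying record. For LBW, using final membership would certainly let post-entry information set a fixed exposure. For PTD it is possible and not prevented.

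Neither the net direction nor the size can be known from the documents. The effect is probably limited: an Aim 5 HR of 1.51 would read about 1.50-1.49 if 1-3% of Cohort C were recorded at 28-39 weeks, and about 1.48-1.41 if 5-15% were. These figures rest on assumed late shares, assumed PTD timing and coding from entry. Delivery-prompted recording would act the other way at a rate nobody has documented. No figure has been computed for LBW or for Aims 1 and 2. The sponsor should settle the rule before analysis, since it decides who belongs to the contrast in Aim 5.

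**What to change.** Add to Sections 3.3.3 and 4.2:

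- **PTD:** take infection status at entry (20 weeks) from records dated on or before entry, including pre-pregnancy history. Code infection as time-dependent: a woman first recorded later contributes to D until the record date and to the infected group from then on.
- **LBW:** use infection status at the 20-week landmark.
- **Delivery:** records dated on or after the delivery admission do not change the cohort.
- **Sensitivity analysis:** repeat the analyses with final (ever-recorded) status.
- **Reporting:** give the number of women first recorded after 20 weeks and the number first recorded at delivery, so that readers can judge the size.

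The cost is SAP wording and use of the dates attached to EMR records. The downside should be stated: some women with latent infection are counted in D before their record date, a small dilution against 79,200, and C loses a few late-recorded women. The sensitivity analysis shows whether either matters.

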4 STATISTICAL METHODS

4.1 General Approach

The study design can be characterized as two-stage, with the first stage sample consisting of 90,000 pregnant women, each of whom will be classified into the four primary exposure categories defined by genital herpes and treatment status (Figure 1). In addition to exposure status, extensive potential confounders as described above (Table 5) will also be measured on the Stage I sample of 90,000 subjects. At the second stage, a random sample of 300 women will be selected within each of the four exposure categories (total N=1,200), for detailed history and characteristics of genital herpes infection, compliance to prescribed medications, and additional confounder/effect modifier assessment prior to delivery. Unlike typical applications of two-stage sampling in epidemiologic studies, where the Stage II sample is selected on the basis of both exposure (or exposure surrogate) and outcome (i.e. two stage case-control sampling), only exposure status will be known at the time of Stage II sampling to keep the nature of a cohort study design (*covariate assessment prior to pregnancy outcome assessment*). However, pregnancy outcomes of interest will eventually be measured on all 90,000 Stage I units, and *we will utilize all available information in both Stage I and Stage II samples in estimation of associations of interest*. Study Aims will be addressed using logistic regression (LBW) and Cox proportional hazards regression models (PTD)^{48,49}.

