4.2 Estimation

Regression parameter estimates and associated standard errors will be obtained via semiparametric maximum likelihood (SMLE)⁵⁰ utilizing exposure, outcome, and confounder measurements on all 90,000 Stage I units in addition to the additional confounder/effect modifier measurements on the subset sample at Stage II. Thus, our study design can be characterized as a missing data problem, with Stage II covariates only assessed on a subset of the full cohort. Scott and Wild presented a unified method for fitting arbitrary regression models to a large class of missing data and/or response selective sampling problems. These applications are generally characterized as: 1) a set of easily-obtainable variables are measured on a sample of N individuals (Stage I); one or more of these variables are to be used as explanatory in the regression model (e.g. herpes and treatment status), or are informative surrogates for “expensive” variables to be measured on a subsample; 2) the response variable is obtained for all N individuals (e.g. LBW and PTD status) or a subset; and, 3) a set of “expensive” explanatory variables (e.g. details in genital herpes history and characteristic, compliance to treatment, and potential confounders/effect modifiers) are measured on a subsample (Stage II). Parameter estimation is by maximizing the profile likelihood (R software available from the authors), with the estimator shown to be consistent and have full semiparametric efficiency⁵⁰.

Aim 1. Does treating genital herpes infection in pregnant women reduce the risk of adverse pregnancy outcomes including PTD or LBW? (treated vs. untreated)

Point and interval estimates of the hazard ratio for PTD associated with treated genital herpes vs. not treated infection, will be calculated as described above, using Cox regression (Cohort A + B vs. C). In determining potential confounders in our regression models, we will first examine

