4.5 Sample Size and Statistical Power

Given the lack of established methods for power calculations for the SMLE in our two-stage sampling scheme, we provided minimum detectable effect estimates using the results from a simulation study that we have conducted. The study provides information on the expected efficiency gains of the two-stage SMLE, relative to a standard regression analysis of the Stage II sub-sample only (with complete data on all confounders in addition to exposure and PTD/LBW status). For the purposes of our simulation study, we made a few simplifying assumptions. We assumed three exposure categories: no infection, infection with treatment, infection without treatment, with population prevalence set at 87%, 8% and 5% (similar to preliminary data), and outcome relative risks of 1.0 (ref), 1.5 and 2.0, respectively. We assumed one binary confounder measured in the Stage II sub-sample with varying prevalence across exposure categories and strength of association with outcome. The pregnancy outcome incidence was assumed at 8% (among those unexposed to infection). The Stage I sample size was 90,000, with random selection of 300 in each of the two infection/treatment categories. Relative efficiencies [i.e. $\text{Var}(\text{Stage II MLE}) / \text{Var}(\text{SMLE})$] ranged from 4 to 82 across the scenarios, demonstrating substantial gains by utilizing exposure and outcome information in the full sample of 90,000.

As an approximation to the impact of utilizing exposure and outcome information on 90,000 Stage I women in combination with the Stage II sub-sample of 1200 women, we took an “effective sample size” approach, and assumed the worst case among the simulation scenarios considered, where the relative efficiency of the SMLE was approximately 4.0. Thus, rather than basing power calculations on the Stage II sample size of 600 (300 in each group, for a two-group contrast), we based them on 2400 (i.e. $4.0 * 300$; 1,200 in each cohort category). We acknowledge that estimated gains in efficiency are based on results from a simulation study and may vary in actual analysis.

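### Stage II interviews are collected until 300 women per cohort have completed, and the plan treats these completers as a random sample without addressing the 100-129 non-participants per cohort

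*Combined protocol and SAP*

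**What the plan says.** All of this is in the combined protocol and SAP.

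- **Section 3.3.3 (Stage II samples)** expects that "a participation rate of 70-75% among eligible pregnant women can be expected" and then states: "The recruitment will continue until 300 subjects from each of the four cohort groups have completed the interview". It mentions participation bias once, and its answer is to select women mostly before the third trimester so that interviews precede delivery.
- **Section 4.1** describes the outcome of this process as follows: "a random sample of 300 women will be selected within each of the four exposure categories".
- **Section 4.2** frames the analysis thus: "our study design can be characterized as a missing data problem, with Stage II covariates only assessed on a subset of the full cohort". The semiparametric maximum likelihood estimator (SMLE) uses exposure, outcome and confounders on all 90,000 women, plus the Stage II measurements. Under Aim 1, a potential confounder stays in the model if it changes the treatment coefficient by 10% or more.
- **Section 4.5** bases its efficiency simulation on 90,000 women "with random selection of 300 in each of the two infection/treatment categories". It mentions no non-response.
- **Section 4.4 (last paragraph)** expects little or no missing data and offers multiple imputation if needed. It does not mention women who decline the interview.
- **Section 5.4** provides a refusal card, followed by telephone contact with those who do not return it. It plans no analysis of refusers.

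**The concern.** Recruiting to a target number of completions restores the count but not the randomness. Stage II exists to supply what the medical record lacks: detailed infection history and severity, compliance, multivitamin use and physical activity. In the SMLE the completers inform the distribution of these covariates for every woman not interviewed. If completers differ from non-participants on them, and the modelled Stage I variables do not explain the difference, the Stage II adjustment is wrong.

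The error matters most when the response pattern differs between the cohorts being compared, and the plan gives reasons to expect that it may:

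- Under section 3.1, Cohorts A, B and C are asked about herpes history, A and B also about compliance, and D about neither.
- Cohort B is first treated in the third trimester, so its status cannot be confirmed until then, although Stage II selection is meant to happen mostly earlier. Women confirmed as B would be reached nearer to delivery.

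Aims 1, 2 and 5 all compare across these cohorts. Compliance is measured only in treated completers, so an error there has no counterpart in the untreated group to offset it.

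**Working it through.** **1. The plan's own figure.** Section 4.5 takes the worst simulated case, "where the relative efficiency of the SMLE was approximately 4.0". Effective size = 4.0 × 300 = 1,200 per cohort, or 2,400 for a two-group contrast. This reproduces. Table 6 follows from it when the stated rate is read as the overall rate. For example, Aim 2 with PTD 11% and HR 0.71 has 2,400 × 0.11 = 264 events, and power = Φ(√(264 × 0.25) × |ln 0.71| − 1.96) = 0.795. Ten of the twelve cells come within 2 points of 0.80. The other two (0.770 and 0.821) have detectable HRs within 0.01 of those stated. Table 6 rests on 300 completers, which is what the recruitment rule delivers.

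**2. Women approached.** Number approached = 300 / participation.

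| Participation | Approached per cohort | Non-participants per cohort | Non-participants, four cohorts |
|---|---|---|---|
| 75% | 300/0.75 = 400 | 100 | 400 |
| 70% | 300/0.70 = 429 | 129 | 516 |

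Had only 300 been drawn, 210-225 interviews per cohort would result.

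**3. When the SMLE is biased.** It remains valid if, given exposure, outcome and the Stage I variables in the model, participation is unrelated to the Stage II covariates. The plan neither states nor checks this condition. The 10% rule judges a covariate by its effect on the treatment coefficient, so it can remove one that predicts participation.

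**4. Possible size (all inputs assumed).** Take a binary Stage II confounder with prevalence p and relative risk RR, and overall participation of 70%. If participation is d lower in women with the confounder, it is r1 = 0.70 − d(1 − p) in those women, and prevalence among completers is q = p × r1 / 0.70. The confounding factor for treated versus untreated is (1 + p_T(RR − 1)) / (1 + p_U(RR − 1)). The residual error is the true factor divided by the factor computed from completers. This is a plug-in calculation, not a run of the SMLE.

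With p = 50% in treated and 30% in untreated women and RR = 2, the true factor is 1.5/1.3 = 1.154.

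| Response pattern | q treated | q untreated | Factor from completers | Residual |
|---|---|---|---|---|
| d = 0.20 in both | 0.429 | 0.240 | 1.152 | 1.002 |
| d = 0.20 in treated only | 0.429 | 0.300 | 1.099 | 1.050 |
| d = 0.10 treated, −0.10 untreated | 0.464 | 0.330 | 1.101 | 1.048 |

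Over RR 1.5-3 and treated prevalence 50-60% (untreated 30%), the residual is 0.986-1.003 when the pattern is the same in both cohorts. When it differs, the residual is 0.925-1.077, and the smallest departure is 2.6%.

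**5. Compliance (assumed).** Suppose true compliance is 70%, with participation of 80% in compliers and 55% in non-compliers. Overall participation is 0.56 + 0.165 = 72.5%, within the plan's range. Completers show 0.56/0.725 = 77% compliance.

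**6. What the fix can recover.**

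- *Outcome alone.* Take prevalence 50% treated and 20% untreated, with participation (with versus without the confounder) 80% versus 65% in treated and 60% versus 75.6% in untreated women. Completers show 0.552 and 0.166. At RR = 2 the factor is 1.331 instead of 1.250, an error of 6.5%. Weighting by cohort and outcome only, with 8% baseline PTD risk, leaves 6.4%. At RR = 3 the error goes from 10.6% to 10.2%.
- *A medical-record predictor.* Suppose half of treated women carry a recorded marker, the confounder is present in 80% with it and 20% without it (overall 50%), and participation is 60% and 80% respectively. Completers then show (0.5 × 0.6 × 0.8 + 0.5 × 0.8 × 0.2)/0.70 = 0.457. With no such dependence in untreated women, the error without the marker is 1.5/1.457 = 1.029 at RR = 2. With the marker in the model it disappears, because the confounder's distribution within each marker level is correct among completers.

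**The case against.** The best defence is that the estimator is already designed for missing data. Section 4.2 uses outcome and confounders on all 90,000 women, so refusal explained by modelled Stage I variables does no harm. Covariates are collected before delivery, so the outcome itself can rarely cause refusal. Early contact, telephone follow-up and the $40 payment should help participation. All of this stands, and it narrows the point to response that depends on Stage II covariates beyond the modelled variables.

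A reader might infer more than the documents support:

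- **That the whole 90,000-woman result is unsound.** Exposure, outcome and medical-record confounders are known for everyone under the Stage I consent waiver. Only the Stage II adjustment is exposed. For Aim 5, herpes history is not asked in Cohort D, so infection severity cannot be an adjustment covariate there.
- **That the likelihood assumes interview completion depends on cohort alone.** It also conditions on outcome and the retained Stage I variables.
- **That replacing refusers causes the bias.** Replacement is itself an inference from the stopping rule and the participation rate. Drawing a fixed 300 would leave the same non-response with fewer interviews.
- **That the imputation in section 4.4 is confined to item missingness.** The text sets no such limit. It simply does not mention interview refusal.
- **That errors of 6.5% or 11% are to be expected.** They need response to run in opposite directions in the two cohorts, and no such figures are in the documents.

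The propensity-score and instrumental-variable analyses are useful cross-checks on confounding, but they do not correct for non-response.

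**Conclusion.** The gap is real but limited. The plan expects 25-30% of approached women not to be interviewed, treats the remainder as random within cohort, and neither states nor checks the assumption that makes this acceptable. Its confounder-selection rule can also discard the variables that would make the assumption more plausible.

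The documents do not determine whether there is bias, in which direction, or how large. On the assumed values above it is about 1% or less when response patterns are alike across cohorts (1.4% at most in the grid) and roughly 3-8% when they differ. These ranges come from a single binary confounder and a plug-in factor. They ignore any protection from the modelled medical-record variables and do not measure what the fix would gain. That gain depends on how well the record predicts participation, which is unknown. Table 6 needs no change on this account. The case for acting is that the repair is cheap and uses data already held.

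**What to change.** 1. In section 3.3.3, require a record of every woman drawn for Stage II, by cohort: completed, refused, not reached, or delivered before contact. This must begin with the first draw.
2. In section 4.2, state the assumption that, within cohort and given outcome and the modelled Stage I variables, completion is unrelated to the Stage II covariates.
3. Model completion within each cohort on the Stage I medical-record covariates. Retain its predictors in the SMLE as Stage I covariates or strata, whatever the 10% rule says.
4. Keep the SMLE as the main estimator. As sensitivity analyses, report a response-weighted analysis and a comparison of completers with non-completers on medical-record covariates and outcome. Making the weighted estimate primary is a debatable trade-off that this concern does not require.
5. State as a limitation that refusal driven by factors outside the medical record remains uncorrected.

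The cost is a tracking field, some SAP wording, one extra model and slightly wider intervals. No additional interviews are needed.
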